rTMS. Furthermore, it is well known that in order to derive a meaningful clinical effect, the application of multiple sessions of rTMS are needed. 2: This will be the first trial testing an accelerated rTMS treatment paradigm using established rTMS doses in an addictions population. This is important as there is a clear dose response effect in rTMS, where larger doses of rTMS result in a larger clinical effect ([name] et al., 2010; McDonald et al., 2011). It is additionally important as OUD and other substance use disordered populations may be difficult to treat using the standard treatment paradigm of one session per day over several weeks. 3: This trial will be the first to use rTMS as an adjunct to standard of care opioid treatment. OUD patients, including Veterans, are difficult to engage in outpatient care. Subsequently, a treatment that encourages retention and integration early in the recovery process could have a significant impact on patient outcomes.

RESEARCH DESIGN AND METHODS

Approach Overview (Figure 3): Participants will be recruited from the Ralph H. Johnson VAMC, local VA clinics, and Charleston Center. We will collect data at one week, four weeks, and three months following rTMS completion.

[figure not shown]
Acute Phase: We will screen, consent, enroll, and assess participants during an enrollment session. Following enrollment, each participant will complete baseline measurements of opioid use, opioid craving, pain, and functioning (as outlined below). Following the enrollment session, each participant will be randomized and begin the acute treatment phase of the trial. *Participants will receive a total of six sessions of rTMS on three days during the acute phase of the study over a period of up to three weeks. A period of up to one-week in between treatment days will be allowed to maximize feasibility of intervention deliverability in this population while minimizing risk of a treatment gap that is too long to allow for a summation of effect.* On the third treatment day, pain assessments will be repeated. Craving and pain will be assessed using validated questionnaires.

Continuation Phase: Participants will return at one week, four weeks, and three months for follow-up visits to preliminarily assess the intervention's impact on opioid use, pain, and functional outcomes.

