rTMS Treatments: rTMS will be delivered via a MagPro double blinded rTMS Research System (MagVenture, Denmark) with a Cool-B65 Butterfly Coil (a combined active and sham coil). We will use a standard resting motor threshold (rMT) determination to determine the TMS dose ([name] et al., 2006). Treatment will be delivered at 120% rMT. Each active rTMS treatment will consist of a total of 600 pulses of 50 Hz triplets for 2s, and repeated every 10s for a total of 190s of stimulation. Treatments will be delivered at the EEG coordinate for F3 (approximating the left DLPFC), and will be found using the Beam-F3 method (Beam et al., 2009). This is a treatment paradigm that has been used extensively in other trials ([name] et al., 2008; Short et al., 2011; [name] et al., 2014; Li et al., 2013). Sham sessions will be delivered using an electronic sham system consisting of a coil that mimics the appearance and sound of TMS, combined with a TENS device which produces a small electric shock mimicking the feeling of real rTMS. This type of sham has been demonstrated to be indistinguishable from real rTMS, has been well tolerated ([name] et al., 2010; [name] et al., 2014) and successfully used in other clinical trials ([name] et al., 2008; Arana et al., 2008). During each session of rTMS we will present a series of opioid related images, including those utilized in previous studies (Garland et al., 2015; Garland & Howard, 2014). The application of drug cues during rTMS appears to enhance its efficacy (Dinur-Klein et al., 2014). Opiate craving and stress will be assessed before and after each TMS treatment.

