Statistical Analysis: *Study feasibility will be primarily measured by a) the total number of rTMS sessions completed (out of 18 total sessions) b) the proportion of participants completing all of the rTMS session and c) the proportion of participants completing all of the rTMS sessions as well as the follow-up visits. Study tolerability will be measured as the total number of treatment emergent adverse events. Group differences (active rTMS vs. sham rTMS) in the feasibility and tolerability measures will be estimated using generalized linear models with appropriate distributions (Negative binomial for session and AE count and logit for study treatment completion). In addition to study feasibility, efficacy measures (opioid use amounts, pain, and sleep quality) will be estimated for the entire cohort as well as estimates of between group differences. Changes in study efficacy outcomes from baseline to follow-up visits will be estimated and analyzed using appropriate statistical approaches. When parametric modeling assumptions can be made, changes over time and associated variability will be estimated between treatment groups using general linear mixed models (GLMMs). The GLMMs will allow us to estimate group-specific changes over time and overall effect sizes, along with the variation in those measures, while controlling for relevant baseline covariates (e.g. baseline craving, morphine equivalents, withdrawal). Although we will likely not be powered to detect between-group differences in binary outcomes (i.e. any drug use), such effects will be explored using generalized mixed models, and for time-to-event data (e.g. days to first opioid use), survival analysis models will be constructed. When parametric modeling assumptions do not appear to be valid, alternative (e.g. non-parametric) approaches will be used. Efficacy outcomes will also be analyzed for evidence of differential treatment effects in subgroups determined by gender, race, and ethnicity. Post-hoc exploratory analyses using GLMMs within the active rTMS group will address whether specific characteristics (e.g. demographics, baseline craving, morphine equivalents, withdrawal, PTSD) are associated with a differential treatment effect. The subgroup-specific treatment effects and corresponding confidence intervals will be constructed and will be interpreted in terms of their clinical, rather than statistical, significance, and effect size of treatment to inform future trials will be estimated.* **Missing Data and Attrition:** *Missing data in longitudinal studies can be a problematic feature but can be mitigated through study design considerations. We will make every effort to prevent attrition, e.g., telephone/text/e-mail reminders prior to visits, and reinforcing attendance at each visit. However, these methods do not ensure that all data will be collected, and appropriate analysis methods will be employed to accommodate missing data. Maximum likelihood estimation yields valid inferences assuming ignorable attrition (i.e., attrition is accounted for by covariates or the dependent variable measured prior to dropout). In addition, in keeping with the ITT, we will make every effort to continue assessments for the entire course of randomized treatment, even among those who stop participating in the study assigned intervention or fail to complete the full rTMS time course.*

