c. Potential Risks and Risk Mitigation Strategies:

Potential risks of rTMS: The use of high frequency rTMS has been FDA approved for the treatment of major depressive disorder since 2008. Our stimulation parameters (3000 pulses, 10Hz, 5-Seconds on 10-Seconds off) are nearly identical to the FDA approved protocol (3000 pulses, 10Hz, 4-Seconds On, 8-Seconds off), and have been used safely in many investigations including those in depression, pain, and addictions. We chose to use the slightly longer train duration of 5-seconds rather than 4-seconds due to its safety and efficacy in many trials including our preliminary single session trial with opioid users.

The common clinical dose of rTMS in depression is 36 treatments with 3000 pulses per treatment, for a total of 108,000 pulses. We will deliver a total of 18 treatments over 5 days with 3,000 pulses per treatment, for a total of 54,000 pulses. We subsequently will be giving a substantially lower total dose to each participant than is commonly given to patients being treated for depression. Accelerated treatment paradigms (including those with 6 treatments delivered daily) have been safely delivered in both depression and addictions populations without any clear adverse effect.

Risk of Seizure: The most serious risk associated with the use of rTMS is seizure. Since the adoption and widespread use of standard safety guidelines in 1997, there has only been one documented seizure. The risk of seizure has been estimated to be less than 0.1% which is lower than the risk of seizure associated with pharmacologic antidepressants. The risk of seizure is related to the various stimulation parameters (intensity,frequency, train duration), location of application, pre-existing risk of seizure, and substance/medication factors. In the very rare event a seizure is caused, removing the coil is typically sufficient to stop the seizure, and there is no increased risk of subsequent seizure. In order to mitigate the risk of seizure we will carefully individualize the intensity of stimulus (by performing a resting motor threshold determination), treat using standard treatment protocols (used safely in other studies), and exclude potential participants at higher risk of seizure (those with a past history of seizures, those in withdrawal from alcohol or benzodiazepines, etc).

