Risk of Site discomfort and headache: Two relatively common risks associated with the use of rTMS include the risk of mild transient site discomfort during treatment (most patients), and the risk of headache (Approximately 5%) following treatment. Both of these potential side effects are typically mild. In terms of mitigating site discomfort, we will slowly ramp up stimulation intensity during the first three sessions. In our experience both clinically and experimentally this is a successful strategy. Additionally, due to the anti-pain effect of rTMS, participants rapidly adjust to stimulation. In the unusual circumstance that a headache is

caused by rTMS, over the counter analgesics are sufficient to alleviate the headaches, and will be available to patients on the inpatient unit.

Potential hearing loss: The discharge of the rTMS coil generates a high-energy click that may cause cochlear damage. Humans exposed to rTMS have shown temporary increases in auditory threshold (especially at high frequencies) lasting at least 5 minutes and less than 4 hours. Foam earplugs can protect against these changes and will be worn during rTMS sessions.

Safety in the case of pregnancy: This protocol will exclude pregnant women. Pregnancy status will be confirmed as part of the standard screening process.

Pain task: The pain task may cause discomfort but will not cause injury. The task will be stopped when it becomes painful to the participant.

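### The plan states a fixed 120% rMT in one place and a ramp over the first three sessions in another, and its completion measures would not show which intensity was delivered

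*Combined protocol and SAP*

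**What the plan says.** - **Intensity.** rTMS Treatments: "Treatment will be delivered at 120% rMT". No ramp or exception is given.
- **Ramp.** Section 1.c, Risk of Site discomfort and headache, offers a mitigation: "we will slowly ramp up stimulation intensity during the first three sessions". It gives no starting level, steps or end level, and does not refer to rTMS Treatments.
- **Number of sessions.** Acute Phase: "Participants will receive a total of six sessions of rTMS on three days during the acute phase of the study". Statistical Analysis uses a different denominator, "the total number of rTMS sessions completed (out of 18 total sessions". Section 1.c, Potential risks of rTMS, agrees with 18 but on another schedule and pulse count: "We will deliver a total of 18 treatments over 5 days with 3,000 pulses per treatment, for a total of 54,000 pulses".
- **Pulses per session.** rTMS Treatments: "Each active rTMS treatment will consist of a total of 600 pulses of 50 Hz triplets for 2s".
- **Outcomes that depend on sessions.** Feasibility is the number of sessions completed, "the proportion of participants completing all of the rTMS session", and the proportion who complete both the sessions and the follow-up visits. Tolerability is the count of treatment-emergent adverse events. A completed session is not defined, and delivered intensity is not mentioned.
- **Data capture.** Table 1 has no row for delivered intensity. Data management is referred to a DMAP that is not among the documents.

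**The concern.** Feasibility and tolerability are what this 20-participant pilot is chiefly meant to show. Both depend on what was delivered in each session. The ramp exists to reduce discomfort, which the risk section expects in most patients. The adverse-event count in early sessions may therefore depend on whether an operator starts at 120% rMT or builds up to it. With no ramp schedule in the text, two operators could treat participants differently and both be within the protocol.

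A completion rate alone would then not tell the designers of the next trial whether the intensity in rTMS Treatments could be delivered and tolerated. The protocol itself argues, under Innovation, that larger rTMS doses have larger effects, and under Sample Size Justification it relies on this trial's estimates to design the larger one. By that reasoning, the delivered intensity should be reported next to the estimates.

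**Working it through.** **1. The plan's own dose figure.** The risk section's total is reproduced: 18 × 3,000 = 54,000 pulses. The course in Acute Phase and rTMS Treatments is 6 × 600 = 3,600 pulses. The documents give no figure for the share of sessions below 120% rMT, so it is derived here.

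**2. Share of sessions affected.** Share = (sessions at least partly below 120% rMT) ÷ (sessions in the course). The numerator depends on how the ramp is read, the denominator on which section is followed.

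| Reading of the ramp | 6 sessions (Acute Phase) | 18 sessions (Statistical Analysis, risk section) |
|---|---|---|
| All first three sessions below target | 3/6 = 50% | 3/18 = 16.7% |
| Target reached at session 3 | 2/6 = 33% | 2/18 = 11.1% |
| Brief ramp inside each of the first three sessions | no whole session below target | no whole session below target |

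In the first row, at 600 pulses per session, 3 × 600 = 1,800 of 3,600 pulses fall in ramped sessions.

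**3. The unit is uncertain.** Table 1 labels its treatment-period column as TMS sessions 1 to 3, although Acute Phase has six sessions on three days. If the risk section also means treatment days, the ramp could extend over all three days, and so over all six sessions. The 50% is therefore an upper bound only when a session means one stimulation session.

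**4. Effect on average intensity (illustration only).** The documents give no starting level. Assume a linear ramp from s% rMT, with s from 80 to 110, in a course of N sessions. This range is an assumption made to show scale, not a proposal.

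- Target reached at session 4: the shortfalls in sessions 1 to 3 are (120 − s) × (1 + 2/3 + 1/3) = 2(120 − s), so the course mean is 120 − 2(120 − s)/N.
- Target reached at session 3: the shortfalls are (120 − s) × (1 + 1/2) = 1.5(120 − s), so the course mean is 120 − 1.5(120 − s)/N.

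The extremes are:

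- N = 6: from 120 − 80/6 = 106.7% rMT (s = 80, target at session 4) to 120 − 15/6 = 117.5% rMT (s = 110, target at session 3).
- N = 18: from 120 − 80/18 = 115.6% rMT to 120 − 15/18 = 119.2% rMT.

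**5. What the completion measures can show.** None of the three feasibility measures has an intensity condition, and a completed session is not defined. A session given below 120% rMT is neither included nor excluded by the text. Two participants with six sessions each, one at 120% rMT throughout and one ramped over three sessions, could have the same values on all three measures.

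**The case against.** The strongest reply is that the two statements are compatible: 120% rMT is the target, and the ramp is the way to reach it. This stands to the extent that a reader who infers that a site cannot follow both goes too far. The fault is under-specification, because the route to the target is not described.

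Three other inferences are tempting, and the documents do not support them:

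- *That below-target sessions count as completed under the plan.* The Statistical Analysis section is silent. All that can be said is that nothing prevents it.
- *That a participant who never tolerated 120% rMT would be scored as a full completer because of the ramp.* The ramp covers only the first three sessions. Lasting intolerance is a different matter.
- *That the issue is wholly separate from the conflict in session and pulse numbers.* The ramp sentence is in the same section as the text on 10 Hz, 18 treatments and 3,000 pulses, and it mentions an inpatient unit. It may belong to a different treatment schedule, though the documents do not say so. It is nonetheless current text presented as a safeguard. If it no longer applies, the risk section needs correcting.

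It can also be said that the intent-to-treat comparison estimates the effect of the assigned regimen, including any planned ramp, and that fewer early discomfort events are the purpose of a ramp. Both are fair. Completion counts also suit the attendance problem that the accelerated schedule is meant to address, so they should not be replaced. None of this tells the reader what the regimen was. Finally, delivered intensity may already be recorded on a treatment form or under the DMAP, so its absence from the documents does not prove that it is not collected.

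**Conclusion.** The point holds as an unreconciled and under-specified intensity rule, with no stated means of showing in the results which intensity was given. If a session is one stimulation session, the share at least partly below 120% rMT is at most 50% of a six-session course or 17% of an 18-session course. It is lower if the target is reached by the third session. It could be higher if a session means a treatment day. Leading with one half alone would mislead, because the completion count is itself written out of 18.

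That the passages are unreconciled is certain. How much this would alter completion, adverse-event or efficacy results cannot be derived from the documents. No sample size, power or significance level is affected. For an exploratory pilot this is a worthwhile and inexpensive clarification, and it does not undermine the design.

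**What to change.** 1. Reconcile rTMS Treatments with Risk of Site discomfort and headache so that one intensity rule applies. Do this together with the conflict in session and pulse numbers between Acute Phase, rTMS Treatments, Statistical Analysis and Potential risks of rTMS. Which rule applies is for the sponsor to decide. State whether a session is a single stimulation session or a treatment day.
2. Record delivered % rMT for each session in both arms (for sham, the intensity set), if the treatment form or DMAP does not already do so.
3. Define a completed session in Statistical Analysis. Keep the three feasibility measures as session-completion measures, and report beside them, by arm, the number of sessions delivered at the stated target intensity.

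The cost is a wording change, at most one field per session and one extra table row. The added row may make delivery look slightly less favourable than the completion rate alone.

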Quantitative Sensory Testing (QST): Three types of pain will be assessed (mechanical pain; diffuse noxious inhibitory control; and thermal pain). First, each participant's mechanical pain threshold will be estimated using a digital pressure algometer. In this procedure (similar to (1)), the middle of the non-dominant supinator muscle will be located and marked (approximately 15% from elbow to wrist), and then pressure from the algometer will be increased at a rate of 10g/second until the participant perceives a shift in sensation from pressure to pain (the pain threshold). This procedure will be repeated three more times (for a total of four trials), with 30-seconds separating trials. Next diffuse noxious inhibitory control (DNIC) will be measured using the same protocol as above, but during mechanical pain assessments, participants will have their dominant hand submerged up to the wrist in a circulating ice water bath maintained at 4.5 degrees C (40 degrees Fahrenheit). After a 2-minute rest interval, thermal pain will be measured using the cold pressor test. During the cold pressor test, each participant will again submerge their dominant hand up to the wrist in a circulating ice water bath maintained at 4.5 degrees C (40 degrees Fahrenheit). On this trial however, they will leave their hand in until: first they perceive the sensation has shifted from cold to pain (pain threshold), and second when they perceive the inability to tolerate the pain (pain tolerance), at which point they will remove their hand. The maximum allowed duration for the cold pressor test will be 300 seconds (5-mins). QST will be done on treatment Days 1 and 3 and at the one-week follow-up.,

Compensation and Retention: Participants will receive \$40 for the screening visit, \$40 for completion of each rTMS day, and \$40 for each follow-up visit. Compensation will be given in the form electronic funds transfer.

Table 1. Assessment Instruments and Schedule

Instrument	Purpose/Domain	Screening	TMS Sessions 1-3	1 wk, 4 wk, follow-up
Informed Consent	Obtain informed consent	X		
Demographics	Characterize sample	X		
M.I.N.I. International Neuropsychiatric Interview	Assess DSM-5 psychiatric disorders	X		
Timeline Follow-Back: TLFB	Assess opioid and other substance use	X	X	X
Urine Drug Screen: UDS	Assess illicit drug use	X	X	X
Alcohol Breathalyzer	Assess alcohol use	X	X	X

Community Reintegration for Servicemembers	Assess community reintegration	X		X

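### The risk text says the pain task stops once it is painful, but the cold pressor procedure continues past pain onset to tolerance, so the two cannot both be followed

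*Combined protocol and SAP*

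**What the plan says.** The two statements are in different parts of the combined protocol and SAP.

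- **Risk text** (section 1, Risks to the Subjects, under Potential Risks and Risk Mitigation Strategies, Pain task). The entry has two sentences. On expected harm it says: "The pain task may cause discomfort but will not cause injury". Its stopping rule is: "The task will be stopped when it becomes painful to the participant". It refers to a single pain task and does not limit itself to one of the tests.
- **Procedure** (Research Design and Methods, Quantitative Sensory Testing). Three tests are described.
  - *Mechanical pain.* Algometer pressure rises "until the participant perceives a shift in sensation from pressure to pain (the pain threshold"). On repetition: "This procedure will be repeated three more times (for a total of four trials), with 30-seconds separating trials".
  - *DNIC.* The same algometer protocol is run, but "participants will have their dominant hand submerged up to the wrist in a circulating ice water bath maintained at 4.5 degrees C".
  - *Cold pressor.* The hand stays in the same kind of bath through two recorded events. The earlier event is described as "first they perceive the sensation has shifted from cold to pain (pain threshold"). The later event, which ends the immersion, is described as "second when they perceive the inability to tolerate the pain (pain tolerance), at which point they will remove their hand". The limit is given as "The maximum allowed duration for the cold pressor test will be 300 seconds (5-mins").

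QST is scheduled on treatment Days 1 and 3 and at the one-week follow-up. The Statistical Analysis section makes feasibility and tolerability primary and names pain only in general terms among the efficacy measures. Table 1 does not list QST.

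**The concern.** The QST paragraph treats pain onset and inability to tolerate pain as two separate events, and it ends the cold pressor test at the second. The risk text ends the pain task at the first. A protocol that defines a tolerance measurement cannot also promise to stop at pain onset.

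Two things are at stake. One is whether the protocol's own description of risk is accurate for a test that every participant is scheduled to undergo. The other is whether cold pressor tolerance can be measured as described. The trial is meant to supply means and variability for a larger study, so it should be clear what each recorded pain variable represents.

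**Working it through.** The plan states no figure that bears on this point, so the check compares the two texts and counts the tests affected.

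**1. Cold pressor, case by case.** Let P be the time to pain onset and L the time at which pain can no longer be tolerated, with L ≥ P. The QST paragraph ends the test at the smaller of L and 300 s. The risk text ends it at P, if P comes before 300 s.

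- *P is 300 s or more.* Both texts end the test at 300 s. There is no conflict.
- *P is below 300 s and L = P.* Both end it at the same moment. There is no conflict.
- *P is below 300 s and L exceeds P.* The risk text ends the test at P, and the QST paragraph continues it. The two cannot both be followed.

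In the third case, immersion after pain onset under the QST paragraph is min(L, 300) − P, which is at most 300 − P seconds. The 300 s covers the whole immersion and is not extra time after pain begins.

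**2. What is observed under each text.** Under the QST paragraph, both P and L are recorded, with L cut off at 300 s. Under the risk text, only P is recorded. L is then known only to be at least P, so tolerance is right-censored at the threshold.

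**3. Algometer.** Each pressure ramp ends at pain onset, so the risk text fits a single ramp, although the ramp is then repeated to a total of four.

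**4. DNIC.** The ramp again ends at onset of pressure pain, but the other hand is in the ice bath. The paragraph states no stop at onset of cold pain. The 300 s maximum is stated for the cold pressor test only, and the text does not say whether the hand comes out between ramps.

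An illustration shows why the limit matters. Assume that ramps start at zero and that the mean pressure threshold is T grams. At 10 g/s, four ramps take 4 × T/10 = 0.4T seconds, and three gaps take 3 × 30 = 90 s.

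| Assumption about the hand | Immersion (s) | Reaches 300 s at |
|---|---|---|
| Stays in throughout | 90 + 0.4T | T = 210/0.4 = 525 g |
| Out between ramps (cumulative) | 0.4T | T = 300/0.4 = 750 g |

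The documents give no value for T, so this shows only that the question is open.

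**5. Count.** 20 participants × 3 QST occasions = 60 cold pressor tests with full attendance. The Sample Size Justification expects at least 16 completers, who would contribute 16 × 3 = 48 if they attended every QST visit. Sixty is therefore a ceiling.

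**6. Search for a reconciling statement.** Section 2, Adequacy of Protection Against Risks, gives participants the right to withdraw at any time. That right is voluntary and is not a rule that the task stops at pain onset. Nothing else in the documents limits the risk sentence to the algometer or qualifies it for the tolerance measurement.

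**The case against.** The best case for leaving the text alone is that the QST paragraph is the only operational description. The risk entry is a short summary with no apparatus, timing or endpoint, and staff would run the test from the procedure. That is plausible, and nothing in the documents shows that staff would follow different rules or that the arms would be treated differently. But it explains how the test would probably be run. It does not make the risk sentence true.

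One might also read painful as too painful. The text does not say so, and the QST paragraph itself separates the two ideas.

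Several stronger readings are tempting, and the documents do not support them.

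- *Participants and the IRB are misled.* The consent form is not among the documents available here, and section 2 says that it describes the procedures in detail. The IRB reviews the protocol, which includes the tolerance endpoint and the 300 s maximum. What can be shown is an inconsistency within the protocol.
- *A planned efficacy outcome is lost.* Tolerance is measured, but the Statistical Analysis section does not name it. Stopping the cold pressor at onset would still leave the algometer threshold and the cold threshold.
- *Tolerance would equal threshold for everyone.* It would be unobserved beyond the threshold, which is a different thing.
- *All ice-water tests need one common rule and limit.* DNIC and cold pressor have different endpoints, and nothing in the documents requires them to share a rule.

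**Conclusion.** The contradiction stands. For the cold pressor test, the risk text and the QST paragraph cannot both be followed whenever tolerance time exceeds a threshold time that falls below 300 s. Either tolerance cannot be observed, or the risk statement is untrue for this test. The risk statement is not reflected in the DNIC procedure either, where no stop at cold pain is given and the reach of the 300 s maximum is not stated.

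The conflict covers each scheduled cold pressor test on Day 1, Day 3 and at one week, at most 60 in 20 participants. The statistical consequence is limited to one measured variable with no analysis of its own, and no primary analysis is affected. The conclusion assumes that the risk sentence means what it says and covers all the pain tests, since nothing narrows it. It does not depend on the DNIC illustration.

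**What to change.** The sponsor should reconcile the Pain task entry in the risk section with the QST paragraph, for both the cold pressor and the DNIC trials, so that the procedure, the risk text and the list of measured pain variables agree.

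- If the procedure is to stop at pain onset, cold pressor tolerance should be removed as a measured variable.
- If it is to continue to tolerance, the risk statement should be corrected to say so.
- For DNIC, the text should state what stopping rule applies to the immersed hand and whether the 300 s maximum covers it.

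Which rule or limit to keep is for the sponsor and investigators, and this review takes no view on it. The change is to protocol and risk-text wording. It needs no change to sample size, visits or the primary analysis. The sponsor should also check that the consent form agrees with the reconciled text.
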